4.3. Removal of Subjects from Treatment

In accordance with the current revision of the Declaration of Helsinki and other applicable regulations, a subject has the right to withdraw from the study at any time and for any reason without prejudice to his or her future medical care by the physician or at the institution. A subject's participation may also be discontinued by the Investigator or Sponsor due to compliance, safety, or other administrative reason (see also [Section 6.2.12](#)).

The subject **must** be discontinued from the study for the occurrence of an unacceptable toxicity, including any of the following:

- ALT or AST $> 8 \times$ ULN; ALT or AST $> 5 \times$ ULN for > 2 weeks; or ALT or AST $> 3 \times$ ULN and total bilirubin $> 2 \times$ ULN or INR > 1.5 ; or ALT or AST $> 3 \times$ ULN with the appearance of worsening of fatigue, nausea, vomiting, right upper quadrant pain or tenderness, fever, rash, or eosinophilia.

Refer to [Section 3.1.4](#) for details regarding follow-up after early discontinuation. Additional care and treatment will be provided to subjects once study discontinuation, including any required follow-up visits for resolution for study-related AEs, is completed.

Subjects who withdraw from the study treatment and/or study for a reason prior to Day 21 will be replaced.

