6.2.12. Withdrawal of Subjects

A subject may be discontinued from study treatment at any time if the subject, the Investigator, or the Sponsor feels that it is not in the subject's best interest to continue. The following is a list of possible reasons for study treatment discontinuation:

- Subject withdrawal of consent (or assent)
- Subject lacks ability to provide continued informed consent (or assent) and/or sound judgement as to whether to continue in the study
- Subject develops active suicidal ideations or attempts suicide
- Subject is not compliant with study procedures

- AE that in the opinion of the Investigator would be in the best interest of the subject to discontinue study treatment
- Protocol violation requiring discontinuation of study treatment
- Lost to follow-up
- Sponsor request for early termination of study

If a subject is withdrawn from treatment due to an AE, the subject will be followed and treated by the Investigator until the abnormal parameter or symptom has resolved or stabilized.

A subject may be withdrawn from the study at any time if the subject, the Investigator, or the Sponsor feels that it is not in the subject's best interest to continue.

All subjects are free to withdraw from participation at any time, for any reason, specified or unspecified, and without prejudice.

Reasonable attempts will be made by the Investigator to provide a reason for subject withdrawals. The reason for the subject's withdrawal from the study will be specified in the subject's source documents.

Subjects who withdraw from the study treatment and/or study for a reason prior to Day 21 will be replaced.

Refer to [Table 6-1](#) for assessments to be performed for subjects who prematurely discontinue study drug.

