#### **6.2.15 Columbia-Suicide Severity Rating Scale (C-SSRS)**

The C-SSRS is a clinician-administered instrument that assesses suicidal ideation and behavior (38TPosner, 201138T).

The following outcomes are C-SSRS categories and have binary responses (yes/no). The categories have been re-ordered from the actual scale to facilitate the definition of composite endpoints:

Category 1	Wish to be Dead
Category 2	Non-specific Active Suicidal Thoughts
Category 3	Active Suicidal Ideation with Any Methods (Not Plan) without Intent to Act
Category 4	Active Suicidal Ideation with Some Intent to Act, without Specific Plan
Category 5	Active Suicidal Ideation with Specific Plan and Intent
Category 6	Preparatory Acts or Behavior
Category 7	Aborted Attempt
Category 8	Interrupted Attempt
Category 9	Actual Attempt (non fatal)
Category 10	Completed Suicide

Suicidal Ideation since baseline – A “yes” answer at any time during double blind treatment to any one of the 5 suicidal ideation questions (categories 1-5) on the C-SSRS.

Suicidal Behavior since baseline – A “yes” answer at any time during double blind treatment to any one of the 5 suicidal behavior questions (categories 6-10) on the C-SSRS.

There will be no imputation of missing data for C-SSRS.

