### **Liver Function Parameter**

The number and percentage of subjects meeting certain liver function abnormality categories will be summarized by visit:

- Alanine Aminotransferase (ALT) assessment > 3 times upper limit of normal (ULN),

- Aspartate aminotransferase (AST) > 3xULN,
- ALT or AST: > 3xULN; > 10xULN; > 20xULN
- Total Bilirubin: > 1.5xULN; > 2xULN
- Alkaline Phosphatase: > 1.5xULN; >2xULN
- (ALT or AST > 3xULN) and total bilirubin>2xULN
- (ALT or AST>3xULN) and total bilirubin>2xULN and alkaline phosphatase<2xULN

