### Coagulation Parameter Abnormalities

- International Normalized Ratio (INR) >1.5

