16.2.8.1.1	Hematology Results (Enrolled Subjects)	IP	

Listing Number	Listing Title	Validation Method	Shell Number (if repeat)
16.2.8.1.2	Chemistry Results (Enrolled Subjects)	IP	
16.2.8.1.3	Coagulation Results (Enrolled Subjects)	IP	
16.2.8.1.4	Clinically Significant Laboratory Results (Enrolled Subjects)	IP	
16.2.8.1.5	Laboratory Liver Function and Coagulation Parameter Abnormalities (Enrolled Subjects)	IP	
16.2.8.2	Vital Signs (Enrolled Subjects)	IP	
16.2.8.3	12-lead ECG Parameters (Enrolled Subjects)	IP	
16.2.8.4	Physical Examination, Abnormal Results (Enrolled Subjects)	IP	
16.2.8.5	Columbia Suicide Severity Rating Scale (C-SSRS) Questionnaire (Enrolled Subjects)	IP	

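### SAP 6.13 gives no by-arm count of subjects who meet most of the Protocol 4.3 liver discontinuation thresholds, and no by-arm summary of the C-SSRS outcomes defined in SAP 6.2.15

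*SAP*

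**What the plan says.** **Liver, protocol.** Under Protocol 4.3 a subject must "be discontinued from the study for the occurrence of an unacceptable toxicity, including any of the following". The list opens with "ALT or AST $> 8 \times$ ULN; ALT or AST $> 5 \times$ ULN for > 2 weeks". It goes on to ALT or AST above 3x ULN with either total bilirubin above 2x ULN or INR above 1.5, and to ALT or AST above 3x ULN with symptoms, rash or eosinophilia.

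**Liver, SAP.** SAP 6.13.2 (Liver Function Parameter) summarizes, by visit, ALT above 3x ULN, AST above 3x ULN, and "ALT or AST: > 3xULN; > 10xULN; > 20xULN". It also has above 3x ULN with bilirubin above 2x ULN, with and without an alkaline phosphatase condition. The coagulation row is "International Normalized Ratio (INR) >1.5", not linked to transaminases. All of this goes into Table 14.3.4.7. Presentation by arm rests on the general convention in SAP 6.3. SAP 6.2.17 keeps post-baseline repeat and unscheduled laboratory values out of tables and only lists them.

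**Suicidality.** Protocol 6.2.12 gives "Subject develops active suicidal ideations or attempts suicide" as one of the possible reasons for stopping treatment. SAP 6.2.15 defines suicidal ideation since baseline as a yes "answer at any time during double blind treatment to any one of the 5 suicidal ideation questions (categories 1-5) on the C-SSRS", and defines suicidal behavior in the same way from categories 6 to 10. SAP 6.13 has no C-SSRS subsection, and section 14.3.7 of the output list holds only ECG tables. The one C-SSRS output is Listing 16.2.8.5, "Columbia Suicide Severity Rating Scale (C-SSRS) Questionnaire (Enrolled Subjects)".

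**The concern.** The cut-points in the SAP table do not line up with those on which the protocol acts. Between 3x and 10x ULN, where the protocol's 5x and 8x levels lie, the table does not separate subjects. Two outcomes are derived for the C-SSRS and then used in no table.

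Transaminase increase is a known human signal for this drug: Protocol 3.2.1.2 reports it in 10% to 15% of patients in an earlier RA study at 250 mg BID. SAP sections 7 and 8 plan no formal interim analysis and no DSMB analysis, so the final tables are the only planned comparison of safety by arm. A reader of those tables would want to know how many subjects per arm reached a mandatory liver threshold, and how many reported suicidal ideation or behavior. The tables as specified do not say.

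**Working it through.** The plan states no figure on this point, so the check sets the two documents side by side.

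**1. Protocol 4.3 criteria against SAP 6.13.2 rows**

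| Protocol 4.3 criterion | SAP row that counts it |
|---|---|
| ALT or AST >8x ULN | none |
| ALT or AST >5x ULN for >2 weeks | none |
| ALT or AST >3x ULN and bilirubin >2x ULN | yes |
| ALT or AST >3x ULN and INR >1.5 | none (each part counted separately) |
| ALT or AST >3x ULN with symptoms, rash or eosinophilia | none |

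Coverage is 1 of 5.

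**2. Where a peak value lands**

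| Peak ALT or AST | SAP rows met (>3x, >10x, >20x) | Protocol levels passed (3x, 5x, 8x) |
|---|---|---|
| 4x | >3x | 3x |
| 6x | >3x | 3x, 5x |
| 9x | >3x | 3x, 5x, 8x |
| 12x | >3x, >10x | 3x, 5x, 8x |

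Peaks of 4x, 6x and 9x cannot be told apart in these rows, although 9x is a mandatory discontinuation and 4x alone is not.

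**3. By visit, scheduled values only.** The liver rows are by visit, and no any-time count is specified. A subject above 3x at two visits is counted at both, so the number of distinct subjects cannot be read off. As Protocol Table 6-1 reads, chemistry during treatment is on Days 1, 21, 42, 84 and 126. The gaps are 21 − 1 = 20, 42 − 21 = 21, 84 − 42 = 42 and 126 − 84 = 42 days. A rise that lasts just over 2 weeks, or peaks between visits, may show only in repeat tests, which SAP 6.2.17 excludes from tables. Coagulation is scheduled at Screening, Day 84 and Follow-up, so an INR drawn because of a rise at another visit would usually be unscheduled too. New rows would therefore undercount unless 6.2.17 is relaxed for them.

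**4. C-SSRS.** Table 6-1 places the scale at Screening, Day 1, every treatment-period clinic visit and Early Termination. SAP 6.2.15 defines two yes/no outcomes per subject. Tables by arm that use them: 0 of 2.

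**5. What such counts could show with 76 per arm.** With 0 events in 76, the one-sided 95% upper bound is 1 − 0.05^(1/76) = 3.9%. For k events against 0, the two-sided Fisher p-value is 2 × C(76,k)/C(152,k): k = 5 gives 0.058 and k = 6 gives 0.028. The rows would be descriptive and not a powered comparison.

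**The case against.** The strongest reply is that these subjects are already visible by arm. Someone who meets a Protocol 4.3 criterion must be discontinued. A new or worsened laboratory abnormality that leads to discontinuation of investigational product is recorded as an AE (Protocol 7.1.4). TEAEs leading to withdrawal are tabulated (SAP 6.13.1), and so are withdrawal reasons by arm (SAP 6.4). Chemistry summaries include the maximum, Listing 16.2.8.1.5 covers liver and coagulation abnormalities, and listings sort by treatment group. Suicidal events reported as AEs enter the TEAE tables. Protocol 8.6 promises no C-SSRS analysis, nothing requires table cut-points to mirror discontinuation thresholds, and section 6 of the SAP allows extra tables if the data warrant them.

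Much of this stands, and it rules out the reading that liver stops or suicidality go wholly unreported by arm. It does not supply the counts. The withdrawal tables are sorted by preferred term or reason, not by multiple of ULN, and they omit anyone who met a threshold but was not stopped. AE intensity is graded on functioning (Protocol 7.1.5), so a large rise without symptoms could be graded mild. Shift tables use only below, within and above normal. A maximum shows one value, not a number of subjects. Tables added after the data are seen are weaker than rows fixed beforehand.

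Three further inferences are tempting but unsupported:

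- **That the >10x and >20x rows will be almost empty because subjects stop at 8x.** Stopping follows a result and does not cap it. With draws 20 to 42 days apart, a first abnormal value can already exceed 10x, and those rows are legitimate severity categories.
- **That the RA rate predicts how many subjects here will fall in the unseparated band.** Protocol 3.2.1.2 gives no multiple of ULN for that rate. It says RA plasma concentrations were 4- to 5-fold higher than in the Phase 2a AD studies, and it reports no liver test abnormalities in either AD study.
- **That suicidality is a mandatory stop like the liver rule.** Protocol 6.2.12 lists it as a possible reason only.

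**Conclusion.** The gap is real but limited to reporting. Run as written, the SAP gives a by-arm count for 1 of the 5 Protocol 4.3 liver criteria and for neither of the 2 C-SSRS outcomes that it defines. Affected subjects appear only indirectly. The number of subjects involved cannot be estimated from the documents. The primary analysis, its power and its type I error are untouched.

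This rests on the SAP text and its output list being complete as published, and on Table 6-1 having been read correctly from the PDF. The conclusion about missing rows does not depend on Table 6-1; only the point about visit gaps and unscheduled INR values does. No view is taken on which liver threshold is clinically right. It is a cheap improvement worth making, and the unused C-SSRS derivations are the most clear-cut part of it.

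**What to change.** **SAP 6.13.2 and Table 14.3.4.7.** Add number and percentage of subjects by arm, at any time post-baseline, with:

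- ALT or AST >5x ULN;
- ALT or AST >8x ULN;
- ALT or AST >3x ULN with INR >1.5;
- any laboratory criterion of Protocol 4.3, including >5x ULN for >2 weeks, with a stated rule for deriving that duration from dated values.

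For these rows, include repeat and unscheduled values as an explicit exception to SAP 6.2.17. The symptom criterion is not purely a laboratory one. It would need a link to AE data, so a footnote should say that these rows do not cover it.

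**SAP 6.13 and output section 14.3.7.** Add a short C-SSRS subsection and one table: number and percentage by arm with suicidal ideation (categories 1 to 5) and suicidal behavior (categories 6 to 10) during treatment, beside baseline status.

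**Cost.** A few programmed rows, one extra table and one sentence of exception. The data are already collected, nothing changes for sites or subjects, and the existing >10x and >20x rows stay.

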### Coagulation Parameter Abnormalities

- International Normalized Ratio (INR) >1.5

### 6.13.3 Vital Signs

Descriptive statistics for observed values and changes from baseline in the following vital signs will be presented by treatment group and visit:

- Systolic blood pressure (mmHg)
- Diastolic blood pressure (mmHg)
- Pulse rate (bpm)
- Respiration rate (breath/min)
- Body temperature (degrees Celsius)
- Body weight (kg)

Box plots for the above vital signs will be provided for changes from Baseline by visit and maximal change.

### 6.13.4 Electrocardiogram Data

Descriptive statistics for observed values and changes from baseline in the following 12-lead ECG variables will be tabulated at each follow-up visit:

- Heart rate (beats/min)
- PR interval (msec)
- RR interval (msec)
- QRS complex (msec)
- QT interval (msec)
- QTc interval (msec)
- QTcF interval (msec) [Fridericia's formula - QTcF]

ECG Result Interpretation (Normal, Abnormal Not Clinically Significant [NCS], and Abnormal Clinically Significant [CS]) will be summarized by treatment group and visit.

The incidence of ECG abnormalities for subjects with any abnormal CS ECG result will be presented by treatment group and visit.

Additionally, the number and percentage of subjects in each treatment group who meet any of the following criteria for QT or QTcF will be tabulated by treatment group and visit.

- Maximum value >450 to 480 msec
- Maximum value >480 to 500 msec
- Maximum value >500 msec
- Maximum increase from baseline >30 to 60 msec
- Maximum increase from baseline >60 msec

Shift tables in relation to the overall interpretation (Normal, Abnormal NCS, and Abnormal CS) from baseline to each follow-up visit will be presented.

Box plots for ECG data will be provided for changes from baseline by visit and maximal change.

### **6.13.5 Physical Examination**

The body systems within the physical examination data will be summarized by treatment group and visit (Abnormal NCS and Abnormal CS). Changes from baseline will also be tabulated. Details of clinically significant findings will be listed.

Descriptive statistics for observed values and changes from baseline in weight will be presented by treatment group and visit.

## **7 INTERIM ANALYSIS**

No formal interim analyses are planned.

## **8 DATA SAFETY MONITORING BOARD ANALYSIS**

No data safety monitoring board (DSMB) analyses are planned.

## **9 CHANGES TO PLANNED PROTOCOL ANALYSIS**

Not applicable.

## 11 LIST OF TABLES, FIGURES AND LISTINGS

The following table includes details of the tables, figures and listings to be included within each section of the eCTD. The eCTD section is shown in bold. The following validation methods maybe used

- Independent programming of numbers and manual review of format (IP)
- Independent programming by statistician of numbers and manual review of format (Stat IP)
- Manual review (MR)
- Code review (CR)

Table Number	Table Title	Validation Method	Shell Number (If Repeat)
14.1	Demographics Data		
14.1.1	Disposition		
14.1.1.1	Subject Disposition, Analysis Population	IP	
14.1.1.2	Subject Disposition, Screen Failures Enrolled Subjects	IP	
14.1.1.3	Inclusion/Exclusion Criteria Not Met Enrolled Subjects	IP	
14.1.1.4.1	Subject Disposition, Early Withdrawals Safety Population	IP	
14.1.1.4.2	Subject Disposition, Early Withdrawals Efficacy Population	IP	14.1.1.4.1
14.1.1.5.1	Number of Subject by Site Safety Population	IP	
14.1.1.5.2	Number of Subject by Site Efficacy Population	IP	14.1.1.5.1
14.1.1.6.1	Number of Subject by Visits Safety Population	IP	
14.1.2	Demographics and Baseline Characteristics		
14.1.2.1.1	Demographics Safety Population	IP	
14.1.2.1.2	Demographics Efficacy Population	IP	14.1.2.1.1
14.1.2.2.1	Baseline Characteristics Safety Population	IP	
14.1.2.2.2	Baseline Characteristics Efficacy Population	IP	14.1.2.2.1
14.1.3	Physical Examinations		

14.1.3.1	Physical Examinations at Screening Safety Population	IP	
14.1.4	Medical History and Prior Medications		
14.1.4.1.1	Prior Medical History Safety Population	IP	
14.1.4.2.1	Ongoing Medical Conditions at Screening Safety Population	IP	
14.1.4.3.1	Prior Medications Safety Population	IP	
14.1.5.1	Major Deviations		
14.1.5.1	Major Protocol Deviations Safety Population	IP	
14.2	Efficacy Data		
14.2.1	Primary Efficacy Endpoint		
14.2.1.1	Hopkins Verbal Learning Test – Revised (HVLTR) Efficacy Population	IP	
14.2.1.2	Combined Change from Baseline in Z-score of Total Recall and Delayed Recall on the Hopkins Verbal Learning Test – Revised (HVLTR) Efficacy Population	Stat IP	
14.2.1.3	Mixed Models for Repeated Measures Analysis of Combined Change from Baseline in Z-score of Total Recall and Delayed Recall on the Hopkins Verbal Learning Test – Revised (HVLTR) Efficacy Population	Stat IP	
14.2.2	Secondary Endpoints		
14.2.2.1	Wechsler Memory Scale (WMS) Subscore Efficacy Population	IP	
14.2.2.2	Wechsler Memory Scale (WMS) Composite and Overall Score Efficacy Population	IP	
14.2.2.3	Mixed Models for Repeated Measures Analysis of Change from Baseline in Wechsler Memory Scale (WMS) Immediate and Delayed Recall Composite Score (0-228) Efficacy Population	Stat IP	14.2.1.3
14.2.2.3.1	Mixed Models for Repeated Measures Analysis of Change from Baseline in Wechsler Memory Scale (WMS) Immediate Composite Score (0-136) Efficacy Population	IP	
14.2.2.3.2	Mixed Models for Repeated Measures Analysis of Change from Baseline in Wechsler Memory	Stat IP	14.2.1.3

	Scale (WMS) Delayed Recall Composite Score (0-92) Efficacy Population		
14.2.2.4	Clinical Dementia Rating (CDR) Efficacy Population	IP	
14.2.2.5	Mixed Models for Repeated Measures Analysis of Change from Baseline in Clinical Dementia Rating Scale-Sum of Boxes (CDR-SB) Efficacy Population	Stat IP	
14.2.2.6	Mini-Mental State Examination (MMSE) Efficacy Population	IP	
14.2.2.7	Analysis of Covariance of Change from Baseline in Mini-Mental State Examination (MMSE) Score Efficacy Population	IP	
14.2.2.8.1	CSF Biomarkers (T-tau, P-tau181, Aβ1-40, Aβ1-42, Neurogranin, Neurofilament Light Chain, pTau/Aβ1-42 Ratio) Efficacy Population	IP	
14.2.2.8.2	Analysis of Covariance of Change from Baseline in CSF Biomarker (T-tau) Efficacy Population	IP	
14.2.2.8.3	Analysis of Covariance of Change from Baseline in CSF Biomarker (P-tau181) Efficacy Population	IP	
14.2.2.8.4	Analysis of Covariance of Change from Baseline in CSF Biomarker (Aβ1-40) Efficacy Population	IP	
14.2.2.8.5	Analysis of Covariance of Change from Baseline in CSF Biomarker (Aβ1-42) Efficacy Population	IP	
14.2.2.8.6	Analysis of Covariance of Change from Baseline in CSF Biomarker (Neurogranin) Efficacy Population	IP	
14.2.2.8.7	Analysis of Covariance of Change from Baseline in CSF Biomarker (Neurofilament Light Chain) Efficacy Population	IP	
14.2.2.8.8	Analysis of Covariance of Change from Baseline in CSF Biomarker (pTau/Aβ1-42 Ratio) Efficacy Population	IP	
14.2.3	Sensitivity Analyses		
14.2.3.1	Hopkins Verbal Learning Test – Revised (HVLTR) Per-Protocol Population	IP	

14.2.3.2	Combined Change from Baseline in Z-score of Total Recall and Delayed Recall on the Hopkins Verbal Learning Test – Revised (HVLTR) Per-Protocol Population	Stat IP	
14.2.3.3	Mixed Models for Repeated Measures Analysis of Combined Change from Baseline in Z-score of Total Recall and Delayed Recall on the Hopkins Verbal Learning Test – Revised (HVLTR) Per-Protocol Population	Stat IP	14.2.1.3
14.2.3.4	Analysis of Covariance of Combined Change from Baseline in Z-score of Total Recall and Delayed Recall on the Hopkins Verbal Learning Test – Revised (HVLTR) Efficacy Population	Stat IP	
14.2.3.5	Analysis of Covariance of Combined Change from Baseline in Z-score of Total Recall and Delayed Recall on the Hopkins Verbal Learning Test – Revised (HVLTR) Per-Protocol Population	Stat IP	
14.2.4	Exploratory Endpoints		
14.2.4.1	Analysis of Covariance of Change from Baseline in Total Recall on the Hopkins Verbal Learning Test – Revised (HVLTR) Efficacy Population	IP	
14.2.4.2	Analysis of Covariance of Change from Baseline in Delayed Recall on the Hopkins Verbal Learning Test – Revised (HVLTR) Efficacy Population	IP	14.2.4.1
14.2.4.3	Analysis of Covariance of Change from Baseline in Retention (%) on the Hopkins Verbal Learning Test – Revised (HVLTR) Efficacy Population	IP	14.2.4.1
14.2.4.4	Analysis of Covariance of Change from Baseline in Recognition on the Hopkins Verbal Learning Test – Revised (HVLTR) Efficacy Population	IP	14.2.4.1
14.2.4.5	Analysis of Covariance of Change from Baseline in Wechsler Memory Scale (WMS) Recognition Composite Tests of Logical Memory II, Verbal Paired Associates II and Visual Reproduction II (0-60) Efficacy Population	IP	14.2.4.1

14.2.4.6.x	Subgroup Analysis of Covariance of Combined Change from Baseline in Z-score of Total Recall and Delayed Recall on the HVLTL-R Efficacy Population	IP	
14.2.4.7	Pearson's Chi-square Test for Responder Efficacy Population	IP	
14.2.5-14.2.6	Subgroup Analyses		
14.2.5.1.1	Hopkins Verbal Learning Test – Revised (HVLTL-R), Cholinesterase Inhibitor or Memantine Efficacy Population	IP	
14.2.5.1.2	Hopkins Verbal Learning Test – Revised (HVLTL-R), No Cholinesterase Inhibitor or Memantine Efficacy Population	IP	
14.2.5.2.1	Combined Change from Baseline in Z-score of Total Recall and Delayed Recall on the Hopkins Verbal Learning Test – Revised (HVLTL-R), Cholinesterase Inhibitor or Memantine Efficacy Population	IP	
14.2.5.2.2	Combined Change from Baseline in Z-score of Total Recall and Delayed Recall on the Hopkins Verbal Learning Test – Revised (HVLTL-R), No Cholinesterase Inhibitor or Memantine Efficacy Population	IP	
14.2.5.3	Mixed Models for Repeated Measures Analysis of Combined Change from Baseline in Z-score of Total Recall and Delayed Recall on the Hopkins Verbal Learning Test – Revised (HVLTL-R) by Background AD-specific Therapy Efficacy Population	IP	
14.2.6.1.1	Wechsler Memory Scale (WMS) Subscore, Cholinesterase Inhibitor or Memantine Efficacy Population	IP	
14.2.6.1.2	Wechsler Memory Scale (WMS) Subscore, No Cholinesterase Inhibitor or Memantine Efficacy Population	IP	

14.2.6.2.1	Wechsler Memory Scale (WMS) Composite and Overall Score, Cholinesterase Inhibitor or Memantine Efficacy Population	IP	
14.2.6.2.2	Wechsler Memory Scale (WMS) Composite and Overall Score, No Cholinesterase Inhibitor or Memantine Efficacy Population	IP	
14.2.6.3	Mixed Models for Repeated Measures Analysis of Change from Baseline in Wechsler Memory Scale (WMS) Immediate and Delayed Recall Composite Score (0-228) by Background AD-specific Therapy Efficacy Population	IP	14.2.5.3
14.2.6.4.1	Clinical Dementia Rating (CDR), Cholinesterase Inhibitor or Memantine Efficacy Population	IP	
14.2.6.4.2	Clinical Dementia Rating (CDR), No Cholinesterase Inhibitor or Memantine Efficacy Population	IP	
14.2.6.5	Mixed Models for Repeated Measures Analysis of Change from Baseline in Clinical Dementia Rating Scale-Sum of Boxes (CDR-SB) by Background AD-specific Therapy Efficacy Population	IP	14.2.5.3
14.2.6.6.1	Mini-Mental State Examination (MMSE), Cholinesterase Inhibitor or Memantine Efficacy Population	IP	
14.2.6.6.2	Mini-Mental State Examination (MMSE), No Cholinesterase Inhibitor or Memantine Efficacy Population	IP	
14.2.6.7	Analysis of Covariance of Change from Baseline in Mini-Mental State Examination (MMSE) Score by Background AD-specific Therapy Efficacy Population	IP	
14.2.6.8.1	CSF Biomarkers (T-tau, P-tau181, A $\beta$ 1-40, A $\beta$ 1-42, Neurogranin, Neurofilament Light Chain, pTau/A $\beta$ 1-42 Ratio), Cholinesterase Inhibitor or Memantine Efficacy Population	IP	
14.2.6.8.1	CSF Biomarkers (T-tau, P-tau181, A $\beta$ 1-40, A $\beta$ 1-42, Neurogranin, Neurofilament Light Chain,	IP	

	pTau/A $\beta$ 1-42 Ratio), No Cholinesterase Inhibitor or Memantine Efficacy Population		
14.2.6.9.1	Analysis of Covariance of Change from Baseline in CSF Biomarker (T-tau) by Background AD-specific Therapy Efficacy Population	IP	14.2.6.7
14.2.6.9.2	Analysis of Covariance of Change from Baseline in CSF Biomarker (P-tau181) by Background AD-specific Therapy Efficacy Population	IP	14.2.6.7
14.2.6.9.3	Analysis of Covariance of Change from Baseline in CSF Biomarker (A $\beta$ 1-40) by Background AD-specific Therapy Efficacy Population	IP	14.2.6.7
14.2.6.9.4	Analysis of Covariance of Change from Baseline in CSF Biomarker (A $\beta$ 1-42) by Background AD-specific Therapy Efficacy Population	IP	14.2.6.7
14.2.6.9.5	Analysis of Covariance of Change from Baseline in CSF Biomarker (Neurogranin) by Background AD-specific Therapy Efficacy Population	IP	14.2.6.7
14.2.6.9.6	Analysis of Covariance of Change from Baseline in CSF Biomarker (Neurofilament Light Chain) by Background AD-specific Therapy Efficacy Population	IP	14.2.6.7
14.2.6.9.7	Analysis of Covariance of Change from Baseline in CSF Biomarker (pTau/A $\beta$ 1-42 Ratio) by Background AD-specific Therapy Efficacy Population	IP	14.2.6.7
14.2.6.10.1	Hopkins Verbal Learning Test – Revised (HVLTR), Baseline Body Weight <80 kg Efficacy Population	IP	
14.2.6.10.2	Hopkins Verbal Learning Test – Revised (HVLTR), Baseline Body Weight $\geq$ 80 kg Efficacy Population	IP	
14.2.6.10.3	Combined Change from Baseline in Z-score of Total Recall and Delayed Recall on the Hopkins Verbal Learning Test – Revised (HVLTR), Baseline Body Weight <80 kg Efficacy Population	IP	
14.2.6.10.4	Combined Change from Baseline in Z-score of Total Recall and Delayed Recall on the Hopkins	IP	

	Verbal Learning Test – Revised (HVLTR), Baseline Body Weight $\geq$ 80 kg Efficacy Population		
14.2.6.10.5	Mixed Models for Repeated Measures Analysis of Combined Change from Baseline in Z-score of Total Recall and Delayed Recall on the Hopkins Verbal Learning Test – Revised (HVLTR) by Baseline Weight Efficacy Population	IP	
14.2.6.11.1	Wechsler Memory Scale (WMS) Subscore, Baseline Body Weight <80 kg Efficacy Population	IP	
14.2.6.11.2	Wechsler Memory Scale (WMS) Subscore, Baseline Body Weight $\geq$ 80 kg Efficacy Population	IP	
14.2.6.11.3	Wechsler Memory Scale (WMS) Composite and Overall Score, Baseline Body Weight <80 kg Efficacy Population	IP	
14.2.6.11.4	Wechsler Memory Scale (WMS) Composite and Overall Score, Baseline Body Weight $\geq$ 80 kg Efficacy Population	IP	
14.2.6.11.5	Mixed Models for Repeated Measures Analysis of Change from Baseline in Wechsler Memory Scale (WMS) Immediate and Delayed Recall Composite Score (0-228) by Baseline Body Weight Efficacy Population	IP	
14.2.6.12.1	Clinical Dementia Rating (CDR), Baseline Body Weight <80 kg Efficacy Population	IP	
14.2.6.12.2	Clinical Dementia Rating (CDR), Baseline Body Weight $\geq$ 80 kg Efficacy Population	IP	
14.2.6.12.3	Mixed Models for Repeated Measures Analysis of Change from Baseline in Clinical Dementia Rating Scale-Sum of Boxes (CDR-SB) by Baseline Body Weight Efficacy Population	IP	
14.2.6.13.1	Mini-Mental State Examination (MMSE), Baseline Body Weight <80 kg Efficacy Population	IP	

14.2.6.13.2	Mini-Mental State Examination (MMSE), Baseline Body Weight $\geq$ 80 kg Efficacy Population	IP	
14.2.6.13.3	Analysis of Covariance of Change from Baseline in Mini-Mental State Examination (MMSE) Score by Baseline Body Weight Efficacy Population	IP	
14.2.6.14.1	Hopkins Verbal Learning Test – Revised (HVLTR), CDR 0.5 Efficacy Population	IP	
14.2.6.14.2	Hopkins Verbal Learning Test – Revised (HVLTR), CDR 1.0 Efficacy Population	IP	
14.2.6.14.3	Combined Change from Baseline in Z-score of Total Recall and Delayed Recall on the Hopkins Verbal Learning Test – Revised (HVLTR), CDR 0.5 Efficacy Population	IP	
14.2.6.14.4	Combined Change from Baseline in Z-score of Total Recall and Delayed Recall on the Hopkins Verbal Learning Test – Revised (HVLTR), CDR 1.0 Efficacy Population	IP	
14.2.6.14.5	Mixed Models for Repeated Measures Analysis of Combined Change from Baseline in Z-score of Total Recall and Delayed Recall on the Hopkins Verbal Learning Test – Revised (HVLTR) by Disease Severity Efficacy Population	IP	
14.2.6.15.1	Wechsler Memory Scale (WMS) Subscore, CDR 0.5 Efficacy Population	IP	
14.2.6.15.2	Wechsler Memory Scale (WMS) Subscore, CDR 1.0 Efficacy Population	IP	
14.2.6.15.3	Wechsler Memory Scale (WMS) Composite and Overall Score, CDR 0.5 Efficacy Population	IP	
14.2.6.15.4	Wechsler Memory Scale (WMS) Composite and Overall Score, CDR 1.0 Efficacy Population	IP	
14.2.6.15.5	Mixed Models for Repeated Measures Analysis of Change from Baseline in Wechsler Memory Scale (WMS) Immediate and Delayed Recall Composite Score (0-228) by Disease Severity Efficacy Population	IP	

14.2.6.16.1	Clinical Dementia Rating (CDR), CDR 0.5 Efficacy Population	IP	
14.2.6.16.2	Clinical Dementia Rating (CDR), CDR 1.0 Efficacy Population	IP	
14.2.6.16.3	Mixed Models for Repeated Measures Analysis of Change from Baseline in Clinical Dementia Rating Scale-Sum of Boxes (CDR-SB) by Disease Severity Efficacy Population	IP	
14.2.6.17.1	Mini-Mental State Examination (MMSE), CDR 0.5 Efficacy Population	IP	
14.2.6.17.2	Mini-Mental State Examination (MMSE), CDR 1.0 Efficacy Population	IP	
14.2.6.17.3	Analysis of Covariance of Change from Baseline in Mini-Mental State Examination (MMSE) Score by Disease Severity Efficacy Population	IP	
14.3	Safety Data		
14.3.1	Displays of Adverse Events		
14.3.1.1	Adverse Events, Overview of Treatment-Emergent Adverse Events (TEAE) Safety Population	IP	
14.3.1.2	Adverse Events, TEAEs by Primary System Organ Class and Preferred Term Safety Population	IP	
14.3.1.3	Adverse Events, TEAEs by Preferred Term Safety Population	IP	
14.3.1.4	Adverse Events, Treatment-Related TEAEs by Primary System Organ Class and Preferred Term Safety Population	IP	
14.3.1.4.1	Adverse Events, TEAEs by Primary System Organ Clas, Preferred Term and Causality Safety Population	IP	14.2.4.1
14.3.1.5	Adverse Events, TEAEs Leading to Discontinuation of Study by Primary System Organ Class and Preferred Term Safety Population	IP	14.2.4.1
14.3.1.6	Adverse Events, Serious TEAEs by Primary System Organ Class and Preferred Term Safety Population	IP	14.2.4.1

14.3.1.7	Adverse Events, Treatment-Related Serious TEAEs by Primary System Organ Class and Preferred Term Safety Population	IP	
14.3.1.8	Adverse Events, TEAEs by Primary System Organ Class, Preferred Term and Maximum Severity Safety Population	IP	
14.3.1.9	Adverse Events, TEAEs [ $\geq 2\%$ ] by Primary System Organ Class and Preferred Term Safety Population	IP	
14.3.2	Listings Of Deaths, Other Serious And Significant Adverse Events		
14.3.2.1	Death, Listing Safety Population	IP	
14.3.2.2	Serious TEAEs, Listing Safety Population	IP	14.3.2.1
14.3.2.3	Treatment-Related TEAEs, Listing Safety Population	IP	14.3.2.1
14.3.2.4	TEAEs Leading to Discontinuation of Study, Listing Safety Population	IP	14.3.2.1
14.3.3	Narratives of Deaths, Other Serious and Certain Other Significant Adverse Events ( This is usually not created by stats but this placeholder )		
14.3.4	Abnormal Laboratory Values		
14.3.4.1	Hematology Safety Population	IP	
14.3.4.2	Shift Table - Hematology Safety Population	IP	
14.3.4.3	Chemistry Safety Population	IP	
14.3.4.4	Shift Table – Chemistry Safety Population	IP	14.3.4.2
14.3.4.5	Coagulation Safety Population	IP	
14.3.4.6	Shift Table – Coagulation Safety Population	IP	14.3.4.2
14.3.4.7	Liver Function Parameter and Coagulation Parameter Abnormalities Safety Population	IP	
14.3.5	Extent Of Exposure, Dosage Information, And Compliance		
14.3.5.1	Study Drug Exposure and Compliance Safety Population	IP	
14.3.6	Vital Signs And Physical Examination		
14.3.6.1	Vital Signs Safety Population	IP	

14.3.6.2	Physical Examinations at Post-baseline Visits Safety Population	IP	
14.3.6.3	Body Weight Safety Population	IP	
14.3.7	Other Safety		
14.3.7.1	12-lead ECG Safety Population	IP	
14.3.7.2	12-lead ECG Result Interpretations Safety Population	IP	
14.3.7.3	12-lead ECG Abnormalities for Subjects with Any Abnormal Clinically Significant ECG Interpretation Safety Population	IP	
14.3.7.4	12-lead ECG – QT, QTc, and QTcF Categories QTcF Categories Safety Population	IP	
14.3.8	Concomitant Medication		
14.3.8.1	Concomitant Medications Safety Population	IP	
14.4	PK Data		
14.4.1.1	Neflamapimod Concentrations by Visit PK Population	IP	
14.4.1.2	Pharmacokinetic Parameters of Neflamapimod PK Population	IP	
14.4.1.3.x	Pharmacokinetic Parameters of Neflamapimod by CYP2C19 Genotype Status PK Population	IP	
14.4.2	Correlation Analysis of PK Parameters and Efficacy Data (Combined Change in Z-score, Change in WMS, CDR-SB) Efficacy Population	IP	
14.4.3	Correlation Analysis of PK Parameters and Change from Baseline in CSF Biomarkers Efficacy Population	IP	

Figure Number	Figure Title	Validation Method	Shell Number (If Repeat)
14.2 Figure	Figure for Efficacy Data		
14.2.1.1	Mean ( $\pm$ SE) Combined Change from Baseline in Z-score of Total Recall and Delayed Recall on the HVLTR by Visit and by Treatment Efficacy Population	IP	

14.2.1.2	Mean ( $\pm$ SE) Change from Baseline in Total Recall on the HVLТ-R by Visit and by Treatment Efficacy Population	IP	14.2.1.1
14.2.1.3	Mean ( $\pm$ SE) Change from Baseline in Delayed Recall on the HVLТ-R by Visit and by Treatment Efficacy Population	IP	14.2.1.1
14.2.2	Mean ( $\pm$ SE) Change from Baseline in Wechsler Memory Scale (WMS) Immediate and Delayed Recall Composite Score by Visit and by Treatment Efficacy Population	IP	14.2.1.1
14.2.3	Mean ( $\pm$ SE) Change from Baseline Clinical Dementia Rating Scale-Sum of Boxes (CDR-SB) by Visit and by Treatment Efficacy Population	IP	14.2.1.1
14.2.4	Mean ( $\pm$ SE) Change from Baseline in Mini-Mental State Examination (MMSE) Score by Visit and by Treatment Efficacy Population	IP	14.2.1.1
14.2.5.1	Box Plot of CSF Biomarker (T-tau) Efficacy Population	IP	
14.2.5.2	Box Plot of CSF Biomarker (P-tau181) Efficacy Population	IP	14.2.5.1
14.2.5.3	Box Plot of CSF Biomarker (A $\beta$ 1-40) Efficacy Population	IP	14.2.5.1
14.2.5.4	Box Plot of CSF Biomarker (A $\beta$ 1-42) Efficacy Population	IP	14.2.5.1
14.2.5.5	Box Plot of CSF Biomarker (Neurofilament Light Chain) Efficacy Population	IP	14.2.5.1
14.2.5.6	Box Plot of CSF Biomarker (pTau/A $\beta$ 1-42 Ratio) Efficacy Population	IP	14.2.5.1
14.2.5.7	Box Plot of CSF Biomarker (Brain derived neurotrophic factor (BDNF)) Efficacy Population	IP	
14.3 Figure	Figure for Safety Data		
14.3.1.1	Box Plot of Change from Baseline in Heart Rate (beats/min) Safety Population	IP	
14.3.1.2	Box Plot of Change from Baseline in PR (msec) Safety Population	IP	14.3.1.1

14.3.1.3	Box Plot of Change from Baseline in RR (msec) Safety Population	IP	14.3.1.1
14.3.1.4	Box Plot of Change from Baseline in QT (msec) Safety Population	IP	14.3.1.1
14.3.1.5	Box Plot of Change from Baseline in QRS (msec) Safety Population	IP	14.3.1.1
14.3.1.6	Box Plot of Change from Baseline in QTcF (msec) Safety Population	IP	14.3.1.1
14.3.1.7	Box Plot of Change from Baseline in QTc (msec) Safety Population	IP	14.3.1.1
14.3.2.1	Box Plot of Change from Baseline in Systolic Blood Pressure (mmHg) Safety Population	IP	
14.3.2.2	Box Plot of Change from Baseline in Diastolic Blood Pressure (mmHg) Safety Population	IP	14.3.2.1
14.3.2.3	Box Plot of Change from Baseline in Pulse Rate (beats/min) Safety Population	IP	14.3.2.1
14.3.2.4	Box Plot of Change from Baseline in Respiration (breaths/min) Safety Population	IP	14.3.2.1
14.3.2.5	Box Plot of Change from Baseline in Weight (kg) Safety Population	IP	14.3.2.1
14.3.2.6	Box Plot of Change from Baseline in in Temperature (C) Safety Population	IP	14.3.2.1
14.4 Figure	Figure for PK and PD Data		
14.4.1	Box Plot of Neflamapimod Concentrations by Visit Safety Population	IP	
14.4.2.1.1	Scatter Plot: CTrough vs. Change from Baseline in CSF Biomarker (T-tau) Efficacy Population	IP	
14.4.2.1.2	Scatter Plot: CTrough vs. Change from Baseline in CSF Biomarker (P-tau181) Efficacy Population	IP	14.4.2.1.1
14.4.2.1.3	Scatter Plot: CTrough vs. Change from Baseline in CSF Biomarker (Aβ1-40) Efficacy Population	IP	14.4.2.1.1
14.4.2.1.4	Scatter Plot: CTrough vs. Change from Baseline in CSF Biomarker (Aβ1-42) Efficacy Population	IP	14.4.2.1.1
14.4.2.1.5	Scatter Plot: CTrough vs. Change from Baseline in CSF Biomarker (Neurofilament light chain) Efficacy Population	IP	14.4.2.1.1

